5.4 Efficacy Analysis

Efficacy results will be reported for the FAS and PP set.

All efficacy analysis will be exploratory.

5.4.1 Response Efficacy Definitions

5.4.1.1 RECIST V.1.1

Overall response according RECIST v1.1 will be obtained from target lesion response, non-target lesion response and new lesions, as follows:

Target Lesions	Non-target Lesions	New Lesions	Overall Response
CR	CR	No	CR
CR	Non-CR/non-PD	No	PR
CR	Not all evaluated	No	PR
PR	Non-CR/Non-PD or not all evaluated	No	PR
SD	Non-CR/Non-PD or not all evaluated	No	SD
Not all evaluated	Non-PD	No	NE
PD	Any	Yes or No	PD
Any	PD	Yes or No	PD
Any	Any	Yes	PD

The following results will be reported in all patients and in patients with measurable disease.

- The unconfirmed Best Overall Response, defined as the best overall response recorded from the start of the study treatment until 35 days after last dose administration date and confirmation of response is not required.
 - o When CR or PR is the best response across all time points, then best overall response will be CR or PR respectively.
 - o When SD is the best response for ≥ 12 weeks the best overall response will be SD ≥ 12 w.
 - o When SD is the best response for < 12 weeks the best overall response will be SD < 12 w.
 - o When non-target disease only and Non-CR/Non-PD is the best response for ≥ 12 weeks the best overall response will be SD ≥ 12 w.
 - o When non-target disease only and Non-CR/Non-PD is the best response for < 12 weeks the best overall response will be SD < 12 w.
 - o When PD is the best response across all time points, best overall response will be PD.
 - o When there is no evaluable tumor assessments best overall response will be NE.
- The confirmed Best Overall Response, defined as the best overall response recorded from the start of the study treatment until 35 days after last dose administration date and confirmation of response is required.
 - o When CR or PR is the best response for ≥ 4 weeks then best overall response will be CR or PR respectively.
 - o When SD is the best response for ≥ 12 weeks the best overall response will be SD ≥ 12 w.
 - o When SD is the best response for < 12 weeks the best overall response will be SD < 12 w.
 - o When non-target disease only and Non-CR/Non-PD is the best response for ≥ 12 weeks the best overall response will be SD ≥ 12 w.
 - o When non-target disease only and Non-CR/Non-PD is the best response for < 12 weeks the best overall response will be SD < 12 w.
 - o When PD is the best response across all time points, best overall response will be PD.
 - o When there is no evaluable tumor assessments best overall response will be NE.
- Unconfirmed Objective Response Rate (ORR) is defined as the proportion of patients with best overall response of unconfirmed CR or unconfirmed PR.
- Unconfirmed Clinical Benefit Rate (CBR) is defined as the proportion of patients with best overall response of unconfirmed CR or unconfirmed PR or SD ≥ 12 w.
- Confirmed Objective Response Rate (ORR) is defined as the proportion of patients with best overall response of confirmed CR or confirmed PR.
- Confirmed Clinical Benefit Rate (CBR) is defined as the proportion of patients with best overall response of confirmed CR or confirmed PR or SD ≥ 12 w.
- PFS is defined as the time from start dose until death by any cause or objective tumor progression according to RECIST v.1.1 or clinical disease progression. Patients with no progression or death will be censored at the date of their last evaluable imaging previous 35 days after last dose administration date. Censoring rules are specified below:

Situation	Date of progression or censoring	Outcome
Progression documented between scheduled visits	Earliest of: 
 • Date of assessment by investigator (if progression is based on clinical criteria); or • Date of assessment showing new lesion (if progression is based on new lesion); 	Progressed

Situation	Date of progression or censoring	Outcome
	or • Date of last radiological assessment of measured lesions (if progression is based on increase in sum of measured lesions).	
Death before first progression disease (PD) assessment	Date of death.	Progressed
Death between adequate assessment visits	Date of death.	Progressed
No progression	Date of last radiological assessment of measured lesions.	Censored
Treatment discontinuation for undocumented progression	Date of last radiological assessment of measured lesions.	Censored
Treatment discontinuation for toxicity or other reason	Date of last radiological assessment of measured lesions.	Censored

- 6-months PFS rate is defined as the proportion of patients who are alive and progression-free at 6 months from the date of first dose of study treatment based on RECIST criteria.
- The Overall Survival (OS) is defined as the time from start dose until death from any cause. Patients with no death will be censored on the last available follow-up date.
- The duration of response (DoR) is defined as the time from start dose of first tumor response (either CR or PR) to disease progression or death due to any cause. The DoR will be calculated for the patients with unconfirmed CR or PR.
- The Time to Progression (TTP) is defined as the time from start dose to objective tumor progression or clinical disease progression (TTP does not include deaths). Patients with no progression will be censored at the date of their last evaluable imaging previous 35 days after last dose administration date.
- The Time to Response (TTR) is defined as the time from start dose to unconfirmed ORR date. Patients without ORR will be censored at the date of their last evaluable imaging previous 35 days after last dose administration date.
- Maximum Tumor Shrinkage (best percentage of change from baseline in the size of target tumor lesions) is defined as the biggest percentage of tumor shrinkage from baseline (obtained from the sum of the largest diameters of the target lesions).

5.4.1.2 irRECIST

The following results will be reported in all patients and in patients with measurable disease:

- The response assessment of the tumor is defined as best response according to:
 - irCR: complete disappearance of all measurable and non-measurable lesions. Lymph nodes must decrease to < 10 mm in short axis. Confirmation of response is not mandatory.
 - irPR: decrease of $\geq 30\%$ in Total Measured Tumor Burden (TMTB) relative to baseline, non-target lesions are irNN, and no unequivocal progression of new non-measurable lesions.
 - irSD: failure to meet criteria for irCR or irPR in the absence of irPD.
 - irNN: no target disease was identified at baseline and at follow-up the patient fails to meet criteria for irCR or irPD.
 - irPD: minimum 20% increase and minimum 5 mm absolute increase in TMTB compared to nadir, or irPD for non-target or new non-measurable lesions. Confirmation of progression is recommended minimum 4 weeks after the first irPD assessment.
 - irNE, used in exceptional cases where insufficient data exists.

- irORR is defined as the proportion of participants with irCR or irPR. Participants who do not have on-study radiographic tumor re-evaluation, who received anti-tumor treatment other than the study medication prior to reaching an irCR or irPR, or who died, progressed, or dropped out for any reason prior to reaching an irCR or irPR will be counted as non-responders in the assessment of irORR.
- irCBR is defined as the proportion of participants with irCR or irPR or irSD. Participants who do not have on-study radiographic tumor re-evaluation, who received anti-tumor treatment other than the study medication prior to reaching an irCR or irPR or irSD, or who died, progressed, or dropped out for any reason prior to reaching an irCR or irPR or irSD will be counted as non-responders in the assessment of irCBR.
- irPFS: is defined as the period from the date of treatment initiation to the date of the first documentation of objective progression of disease (irPD) or death due to any cause in absence of documented irPD. Confirmation of progression is recommended minimum 4 weeks after the first irPD assessment. Participants lacking an evaluation of tumor response after treatment initiation will have their PFS time censored on the date of treatment initiation with the duration of a day. Participants with documentation of irPD or death after a long interval (2 or more incomplete or non-evaluable assessments) since the last tumor assessment will be censored at the time of last objective assessment that did not show PD. The length of irPFS will be calculated as irPFS time (months) = [(progression, death date or censor date) – treatment initiation date +1]/30.4.
- 6-months PFS rate is defined as the proportion of patients who are alive and progression-free at 6 months from the date of first dose of study treatment based on irRECIST criteria.

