	
Clinical assessment. Examination of the penis and/or inguinal region:
 
Radiographic assessment: [computerized tomography (CT) of the chest, abdomen, and pelvis or magnetic resonance imaging (MRI) of the abdomen and pelvis with a non-contrast CT scan of the chest in patients for whom CT scans with contrast are contraindicated] will be performed using RECIST v.1.1 every 8 weeks (\pm 7 days) from the first dose of study treatment up to 6 months (more frequently if clinically indicated). All subjects who remain on treatment for 6 months will subsequently have imaging performed every 12 weeks (\pm 7 days). Imaging should continue to be performed until radiologic evidence of PD, treatment discontinuation, the start of new anti-cancer treatment, withdrawal of consent, death, or the EoS, whichever occurs first. Bone scans will also be used to assess bone metastases. If a subject has a known history of bone metastases or has new bone pain during screening, a bone scan should be obtained prior to study entry. A bone scan at follow-up is required only if they develop new or worsening symptoms or if the site believes they have attained a complete response (CR). If a subject has no known metastatic disease in the bone or active symptoms, a bone scan at baseline is not needed.
 
After PD by RECIST v.1.1, if the site Investigator determines the subject is clinically stable and will benefit from continued treatment, the subject will then be managed by irRECIST.
 
Each assessment will be performed as scheduled according to the calendar regardless of any dosing delay to prevent the introduction of bias into the assessment of efficacy. Failure to perform any of the required disease assessments will result in the inability to determine disease status for that time point.
 
Tumor samples for molecular analysis are required for patient participation and patients must agree to provide tissues from a metastatic site or the primary penile tumor at the time of study entry (that should be available for at least 60% of patients) and at the time of PD. Provision of previous archival tissue is acceptable for patients with non-measurable disease, or inaccessible lesions.
 
Blood samples for molecular analysis will be collected at the time of baseline, after 2 cycles of study treatment (C3D1), and upon PD or EoS.
 
Safety assessments:
 
The occurrence and maximum grade of AEs observed throughout the study will be listed. Any AE that the Investigator reports as unrelated to the drug will also be reported. In this study, AEs will be assessed according to the NCI-CTCAE v.5.0.

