6.4.2 Response Assessment

CBR is defined as the number of patients with CR, partial response (PR) or stable disease (SD) (for at least 12 weeks) divided by the number of patients in the analysis set. Tumor response

will be defined as best response, based on local investigator's assessment according to RECIST criteria guidelines (version 1.1).

ORR is defined as the proportion of the subjects in the analysis set who have a CR or PR based on RECIST v.1.1:

- **CR**: Complete disappearance of all target lesions. Any pathological lymph nodes (target or non-target) must have reduction in short axis to < 10 mm.
- **PR**: At least a 30% decrease in the sum of diameters of target lesions, taking as reference the baseline sum diameters.
- **SD**: Neither sufficient shrinkage to qualify for PR, nor sufficient increase to qualify for PD, taking as reference the smallest sum diameters while on study.
- **PD**: At least a 20% increase in the sum of diameters of target lesions, taking as reference the smallest sum diameters while on study. The development of new, previously undetected lesions is also considered progression.

DoR is defined as the time from first documented CR or PR until disease progression or death from any cause, based on local investigator's assessment according to RECIST criteria v.1.1. In case of the patient first reaching PR and later CR, the duration of CR will be measured and reported separately, starting from the date when first documented, and ending when a progressive disease is diagnosed, or the patient dies.

Maximum tumor shrinkage is defined as the percentage of tumor shrinkage from baseline (obtained from the sum of the largest diameters of the target lesions), based on local investigator's assessment according to RECIST criteria v.1.1.

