8.3 Analysis Sets

Full analysis and safety set.

The full analysis and safety set includes patients who receive at least one dose of study medication.

Per-protocol set

All patients that accomplish selection criteria, receive at least one drug exposure, and receive the protocol required study drug exposure and processing. Criteria for determining the “per protocol” (PP) group assignment would be established by the Steering Committee before the statistical analysis begins. This analysis will only occur if this set differs by $\geq 10\%$ from the full analysis set.

Exploratory analysis set

All patients with biomarker evaluable samples with the assay and alternative platforms that accomplish selection criteria and receive at least one drug exposure.

Analysis set schedule

Primary, secondary and irRECIST endpoints will be analyzed on the full analysis set, and per-protocol populations. Full analysis set will be considered the primary population for the analysis. Biomarker and correlation between biomarkers and clinical outcomes will be analyzed on exploratory analysis set. Safety analysis will be performed on the safety set.

The estimands for the study based on ICH E9 (R1) addendum will be fully described in the statistical analysis plan.

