8.4 Statistical Plan

8.4.1 Primary Efficacy Endpoint

The primary efficacy endpoint for the present study is the ORR. The ORR is defined as the number of patients with CR and PR divided by the number of patients in the analysis set. Tumor response will be defined as best response based on local investigator's assessment according to RECIST criteria v.1.1.

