1.4 Study Design

A total of 18 patients with unresectable locally advanced or metastatic PSqCC will be enrolled into this trial.

INCMGA00012 should be administered intravenously, at flat dose of 500 mg over one hour (\pm 15 minutes) or 30 minutes (-5/+ 15 min) using a filter on day 1 of each 28-day cycle (every 4 weeks). Infusion rate may be reduced if an infusion reaction occurs.

In the absence of progression of disease or unacceptable toxicity, treatment with INCMGA00012 will continue based on physician criteria for up to 2 years.

Tumor assessments per RECIST v.1.1 and irRECIST will be performed approximately every 8 weeks (\pm 7 days) for the first 6 months and every 12 weeks (\pm 7 days) thereafter until PD, treatment discontinuation, the start of new anti-cancer treatment, withdrawal of consent, death, or the end of study (EoS), whichever occurs first. Tumor assessments will be performed on the specified schedule regardless of treatment delays.

The primary endpoint is ORR.

For estimation of ORR, CBR, DoR, PFS, and OS, tumor response will be based on RECIST v.1.1. In patients who continue treatment beyond radiographic PD per RECIST v.1.1, tumor response (ORR, CBR, and PFS) may continue to be assessed using irRECIST criteria until study treatment discontinuation.

Safety assessments will include the incidence, nature, and severity of AEs and laboratory abnormalities graded per the NCI-CTCAE v.5.0. Laboratory safety assessments will include the regular monitoring of hematology, blood chemistry, coagulation, and thyroid function testing.

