5.4.2 Primary Efficacy Analysis

ORR will be estimated with the 95% Clopper-Pearson confidence intervals and the P-value with exact binomial test.

Primary efficacy results will be reported for the FAS and PP set. Full analysis set will be considered the primary set for the analysis.

Table 1. Primary Efficacy Estimands

Estimand	Population	Variable	Intercurrent event strategy	Summary measure
Primary	FAS set	Unconfirmed ORR	- Patient with missing Unconfirmed ORR outcome will be considered as non-responders. - Patients without any post-baseline assessment will be considered as non-responders.	The number and proportion of patients with response with the 95% Pearson-Clopper CI will be calculated.
Sensitivity 1 to Primary	PP set	Unconfirmed ORR	Same as above	Same as above

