5.7 Changes of Analysis from Protocol

- The level of significance α has been changed from \leq to $=$ in some paragraphs.
- We have included the time to response as secondary endpoint. We have dropped the time to progression.

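### Best response is counted only to 35 days after the last dose, so a scheduled scan during a dose hold that ends in discontinuation can drop out of the primary ORR and CBR

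*SAP*

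**What the plan says.** **Window.** SAP 5.4.1.1 takes, for both unconfirmed and confirmed best overall response (BOR), the "best overall response recorded from the start of the study treatment until 35 days after last dose administration date". Unconfirmed ORR (the primary variable) and CBR are proportions of patients with a qualifying BOR. Without an evaluable assessment, BOR is NE.

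**Protocol definition.** Protocol 8.4.1 states "Tumor response will be defined as best response based on local" investigator assessment by RECIST v1.1, with no limit tied to the last dose. Protocol 6.4.2 sets none for CBR either.

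**Estimand.** Protocol 8.3 promises: "The estimands for the study based on ICH E9 (R1) addendum will be fully described in the statistical analysis plan". SAP Table 1 (5.4.2) has two entries under intercurrent events. One is "Patient with missing Unconfirmed ORR outcome will be considered as non-responders"; the other treats patients with no post-baseline assessment in the same way. Treatment discontinuation is not named.

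**Listed changes.** Apart from an edit to the alpha symbol, SAP 5.7 says only: "We have included the time to response as secondary endpoint. We have dropped the time to progression".

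**Scans and holds.** The protocol synopsis says "Each assessment will be performed as scheduled according to the calendar regardless of any dosing delay to prevent the introduction of bias", and SAP 1.4 says "Tumor assessments will be performed on the specified schedule regardless of treatment delays". Scans are every 8 weeks for 6 months, then every 12 weeks (±7 days). Protocol 5.3 allows a toxicity hold of up to 12 weeks.

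**The concern.** The scan clock and the counting clock have different origins. Scans run from the first dose and ignore dosing delays. The BOR window runs from the last dose and is shorter than the gap between scans. During a hold the last-dose date stands still. If dosing resumes, that date moves forward and the scan counts. If the hold ends in discontinuation, the date stays before the hold, and a scan that was required and done while the patient was still on study treatment can be discarded afterwards.

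What decides whether such a response counts is then the number of doses given before the hold, not the disease. The synopsis gives avoidance of bias as the reason for keeping scans on the calendar, and the window partly undoes that.

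The SAP is also uneven. In 5.4.1.2, irORR and irCBR have no 35-day limit: a patient is a non-responder if other anti-tumour treatment, progression, death or dropout comes before response. Maximum tumour shrinkage has no limit either. The same scan could therefore count for irORR and appear in the waterfall plot while the patient is a non-responder for the primary ORR. The planned RECIST/irRECIST comparison would then partly reflect different observation windows.

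**Working it through.** **1. The plan's own figure.** Inputs from SAP 1.6: p0 = 0.05, p1 = 0.25, at least 3 responders of 16, 10% drop-out. Exact binomial: P(X ≥ 3 | 16, 0.05) = 0.0429 and P(X ≥ 3 | 16, 0.25) = 0.803; 16/0.9 = 17.8, so 18 patients. This reproduces.

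**2. The boundary in the primary set.** The full analysis set is everyone dosed, planned as 18. P(X ≥ 3 | 18, 0.05) = 0.0581 and P(X ≥ 4 | 18, 0.05) = 0.0109, so p < 0.05 needs 4 responders. Doubling the p-values (0.116 and 0.022) does not move this boundary. Power at ORR 25% is P(X ≥ 4 | 18, 0.25) = 0.694.

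**3. Calendar.** Count the first dose as day 0. Dose k falls on day 28(k − 1), and the window closes on day 28(k − 1) + 35 = 28k + 7. Scans fall on days 56, 112, 168, 252 and 336. Count the 12-week hold from the last dose (the shorter reading; Protocol 5.4 uses that origin for unresolved toxicity).

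| Last dose k | Dose day | Window closes | Scheduled scan (±7) |
|---|---|---|---|
| 1 | 0 | 35 | 56 (49–63) |
| 3 | 56 | 91 | 112 (105–119) |
| 5 | 112 | 147 | 168 (161–175) |
| 8 | 196 | 231 | 252 (245–259) |
| 11 | 280 | 315 | 336 (329–343) |

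In each row the scan is nominally 56 days after the last dose. Allowing ±7 days for the scan and, for k > 1, ±3 days for the dose, the gap is 46–66 days (49–63 for k = 1): always beyond 35 and always within 84. For k = 2, 4, 7 and 10 a scan falls nominally on day 84 after the last dose, at the edge, and is not counted here. For k = 6, 9 and 12 there is none.

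**4. Consequences.** After one dose, every scheduled scan is outside the window, so BOR is NE and a patient with PR or CR is a non-responder. After dose 3, the window closes on day 91. The first scheduled scan at or beyond 12 weeks is week 16 (days 105–119), so SD of at least 12 weeks cannot be shown on scheduled scans.

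**5. How many patients.** The documents give no rate for this trial. Protocol 1.6.3 reports discontinuation for treatment-emergent adverse events of 9.0%, 7.4% and 10.7% in three larger studies of other populations (0 of 6 in a small one). For 18 patients, 18 × 0.074 = 1.3 and 18 × 0.107 = 1.9. At ORR 25% those patients include 0.25 × 1.3 = 0.33 to 0.25 × 1.9 = 0.48 responders. To be lost, a responder must also have had a hold rather than immediate discontinuation, one of the last-dose numbers above, and a first response only on the dropped scan.

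**6. Power.** Assumption, not in the documents: a share d of true responders is lost. Power is P(X ≥ 4 | 18, 0.25(1 − d)); expected loss is 18 × 0.25 × d.

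| d | Expected lost responses | Power |
|---|---|---|
| 0 | 0 | 0.694 |
| 2% | 0.09 | 0.677 |
| 5% | 0.23 | 0.650 |
| 10% | 0.45 | 0.602 |

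Step 5 puts the 10% row at an extreme: nearly every responder among the adverse-event discontinuations would have to be lost.

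**The case against.** The best defence is that the window is an ordinary on-treatment rule. Protocol 3.2.3 puts the end-of-treatment visit at 28 (±7) days after the last dose, with 35 days as its upper limit. Several passages stop tumour assessment at treatment discontinuation. The protocol sets no observation window for best response, so the SAP had to supply one, and this one is conservative. Most of that stands, though the SAP gives no rationale and the rule still discards scans done before discontinuation.

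Four stronger readings are tempting and are not supported:

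- **That the limit is hidden.** It is written into the definition of the variable that Table 1 names. The gap is that Table 1 does not name discontinuation as an intercurrent event.
- **That SAP 5.7 conceals a change.** The limit is absent from the supplied protocol's definitions and from 5.7, but SAP 1.1 says the SAP was based on protocol version 1.1, which is not supplied. Whether it was a change from that version cannot be judged.
- **That such responses vanish from the report.** irORR and maximum shrinkage would still show them. They are missing from the primary ORR.
- **That scans after discontinuation are lost as well.** This holds only if imaging continues after discontinuation without progression, as Protocol 6.4.4 and footnote 7 of both schedules say. Under the protocol synopsis, 3.1, 6.4.1 and 6.4.3, and SAP 1.4, no such scan is scheduled. The case worked here depends on neither text, because the scan comes before discontinuation.

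**Conclusion.** The point holds for scheduled scans done during a hold that ends in discontinuation, under either imaging text. After last dose 1, 3, 5, 8 or 11 the whole scan window lies beyond day 35 and within the 12-week hold. The error is in one direction: ORR and CBR can only fall, and type I error is not inflated.

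The expected size is very small. If the adverse-event discontinuation rates from other populations carry over, one or two of 18 patients are at risk and well under half a responder is expected among them, so the lower rows of assumed loss (0.694 to 0.677 at 2%) are more plausible than the higher ones. A reader might infer a serious loss of power; the documents do not support that.

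It still deserves correction because the trial is decided on very few responses. One lost response at the boundary moves 4/18 (p = 0.011) to 3/18 (p = 0.058) and reverses the conclusion, and the primary ORR and irORR use different observation windows without explanation.

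**What to change.** - In SAP 5.4.1.1, define BOR, ORR and CBR on all tumour assessments from first dose until the earliest of progression, start of new anticancer therapy, death and end of study. This brings them into line with irORR. State which treatments, including local ones, count as new anticancer therapy.
- In Table 1, name treatment discontinuation as an intercurrent event handled in this way. Keep the 35-day version as a sensitivity analysis and list the rule in SAP 5.7.
- Apply the same end of observation to PFS (5.4.1.1 and Table 2), TTR (5.4.1.1 and Table 2) and DoR (Table 2). Otherwise a responder first seen on day 112 after a last dose on day 56 would be counted in ORR, while his PFS, if he has no event, could be censored at an earlier scan, before his response date.
- Reconcile the passages that end imaging at treatment discontinuation (protocol synopsis, 3.1, 6.4.1, 6.4.3; SAP 1.4) with those that continue it in patients without progression (Protocol 6.4.4, Appendix 1 footnote 7; SAP 1.5 footnote 7).

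The cost is SAP wording for six endpoints, one row in Table 1 and one line in 5.7. Scans during holds are already scheduled, so no new imaging is needed for them. The small downside is that a few off-treatment scans enter an unconfirmed, investigator-assessed endpoint; stopping at new anticancer therapy limits that.

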After progression of disease by RECIST v.1.1, if the site Investigator determines the subject is clinically stable and will benefit from continued treatment, the subject will then be managed by irRECIST as described in **Section 6.4.4** of the protocol.

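### The SAP's RECIST best overall response is not cut at first RECIST progression, so, read literally, a later response in a patient treated beyond progression counts in the primary ORR

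*SAP*

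**What the plan says.** SAP 5.4.2, Table 1, names unconfirmed ORR in the FAS as the primary variable. SAP 5.4.1.1 defines it: "Unconfirmed Objective Response Rate (ORR) is defined as the proportion of patients with best overall response of unconfirmed CR or unconfirmed PR". The window of the unconfirmed version reads: "best overall response recorded from the start of the study treatment until 35 days after last dose administration date and confirmation of response is not" needed. The rule for CR and PR is: "When CR or PR is the best response across all time points, then best overall response will be CR or PR respectively". The confirmed version has the same window.

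Table 1 handles two situations only. A missing response is a non-response, and "Patients without any post-baseline assessment will be considered as non-responders". Progression before response is not listed, and neither is other anticancer therapy.

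Elsewhere the documents close the RECIST series. The Protocol synopsis (efficacy assessments) runs tumor assessments until PD by RECIST v1.1, treatment discontinuation or new anticancer therapy. Protocol 3.1 and 6.4.1 and SAP 1.4 have similar stops. SAP 1.4 adds: "In patients who continue treatment beyond radiographic PD per RECIST v.1.1, tumor response (ORR, CBR, and PFS) may continue to be assessed using irRECIST". Protocol 6.4.1 says the same from the management side. Its condition is "After progression of disease by RECIST v.1.1, if the site Investigator determines the subject is clinically stable and will benefit from continued treatment"; such patients pass to irRECIST.

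For the exploratory irORR, SAP 5.4.1.2 does write exclusions. One covers patients "who received anti-tumor treatment other than the study medication prior to reaching an irCR or irPR". Another covers those "who died, progressed, or dropped out for any reason prior to reaching an irCR or irPR will be counted as non-responders in the assessment of" that endpoint.

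**The concern.** The trial is decided on ORR by RECIST v1.1, so a response that appears only after RECIST progression should not count towards it. The derivation rule nevertheless ties the window to the last dose. Protocol 6.4.4 allows dosing and imaging to continue after first RECIST PD, so for those patients the window stays open past progression.

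A programmer who follows 5.4.1.1 alone would count such a response. One who follows SAP 1.4 would not. In an open-label, investigator-assessed trial of 18 patients, that choice should not be left until the data are known. The planned comparison of RECIST with irRECIST (SAP 5.4.7) would also be blurred, because a response after PD could appear under both.

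**Working it through.** **1. Can a scan after PD fall inside the window?** Yes. Under Protocol 6.4.4 the investigator may continue treatment after first RECIST PD, with repeat imaging at least four weeks later. If PD is not confirmed, treatment may go on with the regular imaging schedule. The window closes only 35 days after the last dose.

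**2. Can such a scan read PR under RECIST?** Protocol 6.4.2 measures PD from the smallest sum on study (at least +20%) and PR from baseline (at least -30%). An example with assumed measurements and no new lesion:
- baseline sum 100 mm;
- week 8 sum 120 mm, which is +20% and reads PD;
- week 16 sum 70 mm, which is -30% from baseline and reads PR in the SAP response table if non-target disease is not progressing.

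The best response across all time points is then PR. The same patient has a PFS event at week 8 and a first response at week 16, so his duration of response would start after his progression.

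**3. When can it not?** The table makes any visit with a new lesion PD. The route therefore needs target growth or non-target progression that later reverses, without a persisting new lesion. Clinically unstable patients stop at first PD (Protocol 6.4.4).

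**4. The plan's own design figure.** Inputs from SAP 1.6: p0 = 0.05, p1 = 0.25, one-sided alpha 0.05, at least 3 responders of 16, and 10% drop-out giving 18. With X ~ Bin(n, p):
- P(X≥3 | 16, 0.05) = 1 - (0.4401 + 0.3706 + 0.1463) = 0.043
- P(X≥3 | 16, 0.25) = 0.803
- 16/0.9 = 17.8, rounded up to 18

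The design reproduces. The proposed cut does not change it.

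**5. Effect of one reclassified patient.** ORR moves by 1/18 = 5.6 points. The one-sided exact p-values against 5% are:
- n = 18: P(X≥3) = 1 - (0.3972 + 0.3763 + 0.1683) = 0.058; P(X≥4) = 0.0581 - 0.0473 = 0.011
- n = 16: P(X≥2) = 1 - (0.4401 + 0.3706) = 0.189; P(X≥3) = 0.043

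One patient changes the verdict between 3 and 4 of 18, or between 2 and 3 of 16.

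**6. Illustration only.** Suppose the true ORR before PD is 5%, and a further 3% or 5% of all patients respond only after PD. These rates are assumed. P(X≥4 | 18) is 0.011 at 5%, 0.051 at 8% and 0.098 at 10%. If the 3% or 5% is instead taken among patients without an earlier response, the rate is 0.05 + 0.95 × 0.03 = 0.0785 or 0.05 + 0.95 × 0.05 = 0.0975, and the results are 0.048 and 0.091.

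**The case against.** The strongest reply is that the RECIST series has already ended. The Protocol synopsis stops assessments at RECIST PD, and SAP 1.4 and Protocol 6.4.1 hand later scans to irRECIST. The phrase about all time points can then mean all RECIST time points. Nothing in the documents says that scans from the irRECIST phase are scored again under RECIST v1.1. This stands to the extent that the documents conflict and do not settle the outcome. It does not remove the gap: the derivation section has its own explicit window, that window runs past PD, and SAP 1.4 says only that irRECIST may be used.

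A reader might infer that responses to the next therapy also count. That route is largely theoretical. Imaging is to stop when new anticancer therapy starts, so a scan would have to be done outside those rules and still fall within 35 days of the last dose.

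A reader might also take the irORR exclusions as proof that the SAP deliberately left the primary endpoint unguarded. They do not show that. The irORR text does not say by which criteria the patient progressed, and if it meant RECIST PD it would exclude the delayed responses that irRECIST is meant to capture. The contrast shows only that such a rule can be written.

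Finally, the margin at 3 versus 4 of 18 arises because a 3-of-16 rule is applied to 18 patients, which is a separate matter. Any single reclassified patient would have the same effect there.

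**Conclusion.** The point holds as an unresolved conflict on the primary endpoint and should be fixed. SAP 5.4.1.1 and Table 1 set no cut at first RECIST PD. Applied literally, they count a CR or PR seen after PD and within 35 days of the last dose, against SAP 1.4 and the Protocol's assessment rules. Any such patient moves ORR upward, by 5.6 points with 18 in the FAS, and could decide the trial at the margin.

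Two stronger conclusions are not supported. The documents do not establish that a response after progression will be counted, because the other reading is available. Nor do they establish a type I error above 5%: they give no frequency of responses after PD, and even the assumed 3% leaves the chance of at least 4/18 near 0.05. The p-values assume 16 or 18 analysed patients and a one-sided exact test against 5%.

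**What to change.** In SAP 5.4.1.1 and Table 1, state that confirmed and unconfirmed RECIST best overall response, and hence ORR, CBR and TTR, use only assessments up to and including the first RECIST v1.1 PD, or before the start of other anticancer therapy, whichever is first. State that later scans feed irRECIST only. Including new therapy costs nothing extra and closes the theoretical route. Applying the same cut to maximum tumor shrinkage, a descriptive variable, is optional.

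The cost is a sentence of SAP text and one program condition. No new data are needed and the sample size is unchanged. The observed ORR may be slightly lower than under the literal rule.
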